Study Design for ACLR subjects: This is a single-center randomized controlled pilot trial of functional resistance training during treadmill walking. Patients with ACLR will be randomized using permuted blocks into one of three groups: 1) functional resistance training with a custom brace during treadmill walking, 2) functional resistance training with elastic bands during treadmill walking, and 3) treadmill walking (sham/control arm). Isometric quadriceps strength symmetry index will be our primary outcome measure. Our secondary outcome measures are: 1) % voluntary activation, 2) knee flexion angle symmetry, 3) knee moment symmetry. Our tertiary outcomes are: 1) patient-reported outcomes via Knee Injury and Osteoarthritis Outcome Score, 2) cortical excitability, and 3) spinal reflex excitability. All outcome measures will be examined at 3 study time points: 1) *Pre-intervention*: about 6 weeks after ACLR (a time-point when adequate quadriceps control is usually achieved), 2) *Post-intervention*: immediately after the intervention, and 3) *Follow-up*: 6-12 months post-ACLR (± 2 weeks) (when patients are typically cleared for return to activity) (Fig. 1).

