H-Reflex Testing: Spinal reflex excitability will be measured with H-reflex testing using a reliable intra- and inter-session protocol ($ICCs > 0.90$)⁵¹ that we have employed previously.^{52,53} Briefly, patients will be positioned supine with the knee supported in flexion and hands at their sides. Factors such as head position, hand movement, etc. may affect the H-reflex so care will be taken to minimize movement. H and M recruitment curves will be mapped for the ACLR limb by applying a 1ms square-wave stimulus to the femoral nerve and recorded using EMG. Stimuli will be delivered by increasing the intensity in 0.2V increments, with a 10-second rest interval after each stimulus until the maximum H-reflex and maximum M-wave are obtained. Three peak-to-peak amplitudes of the maximum H-reflex and M-wave will be recorded and used to create the H-reflex to M-wave ratio.

Analytic Plan: Descriptive statistics will be used to explore the distribution, central tendency, and variation of each measurement, with an emphasis on graphical methods. Normality for each variable will be checked using a Shapiro-Wilks test, and appropriate transformations (e.g., log) will be made when necessary. Linear mixed models will be used to compare the continuous primary and secondary endpoints between the experimental and control arm of the randomized group. Fixed-effects terms will include group, time, group \times time interaction, gender, group \times gender interaction, and other potential covariates such as, age, activity level, and meniscal repair. Patients will be included as random effects in the intercept. A significant main or interaction effect at $\alpha = 0.05$ will be followed by appropriate post-hoc analysis with adjustments for multiple comparisons.

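### Formal arm comparisons are planned as adjusted post-hoc tests behind an unspecified omnibus gate, and no arm-versus-control contrast or confidence interval is prespecified

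*Combined protocol and SAP*

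**What the plan says.** The trial has three arms (brace, elastic band, treadmill walking without resistance). Patients are "randomized using permuted blocks into one of three groups" and measured before the intervention, after it, and at follow-up (Study Design for ACLR subjects). The same section calls it a pilot: "This is a single-center randomized controlled pilot trial of functional resistance training during treadmill walking".

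The Analytic Plan fits a linear mixed model with a random patient intercept to compare outcomes "between the experimental and control arm of the randomized group". That wording is singular, although there are two resistance arms. The listed fixed effects include group, time, gender and two interactions with group. Then comes the rule at issue: "A significant main or interaction effect at" the 0.05 level "will be followed by appropriate post-hoc analysis with adjustments for multiple comparisons".

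The plan does not say which effect licenses which comparison. It names no primary visit, no contrast with control, no confidence interval and no adjustment method. Hypothesis 1 is directed: resistance training should improve strength more than treadmill walking does.

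**The concern.** The hypothesis concerns resistance versus control. A group × time test over three arms and three visits also spends power on differences that nobody hypothesised, such as brace versus band. Putting that test in front of contrasts that are themselves adjusted for multiplicity protects twice against the same error and costs power.

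A pilot also informs the next trial. If arm differences were shown only after a significant omnibus test, the published effects would be those that happened to be large. A non-significant result could then be read as no difference even though the data were compatible with a worthwhile gain.

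**Working it through.** **Figure to reproduce.** None. The documents give no sample size, power, SD, effect size or dropout rate.

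**Inputs from the documents.** 3 arms, 3 visits, random intercept, gate at 0.05, adjusted post-hoc step.

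**Assumed inputs.** SD of the strength symmetry index 15 points; correlation between visits 0.6; both resistance arms truly gain 8 points over control at post and 4 at follow-up; 10, 15 or 20 per arm, equal allocation; no dropout; Bonferroni adjustment.

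**Step 1: degrees of freedom of the gate.** (arms − 1) × (visits − 1) = 2 × 2 = 4. If the two resistance arms are pooled, 1 × 2 = 2.

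**Step 2: precision without a gate.** Within-patient variance = 15² × (1 − 0.6) = 90. The SE of the difference between two arms in pre-to-post change = √(4 × 90 / n).
- n = 10: √36 = 6.0, 95% half-width about 12.0 points
- n = 15: √24 = 4.9, about 9.7 points
- n = 20: √18 = 4.2, about 8.4 points

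These widths are what an unconditional report would give the planner of the next trial.

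**Step 3: simulation of the gate.** Balanced trials were simulated under the random-intercept model. The gate is the 4-df group × time F test at 0.05. The contrasts are each resistance arm versus control in pre-to-post change, using the pooled within-patient error. Success means significance in at least one arm. The same adjustment is used with and without the gate. Results are good to about one percentage point.

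| Setting | 10 per arm | 15 per arm | 20 per arm |
|---|---|---|---|
| Gate opens | 18% | 27% | 36% |
| Bonferroni over two: no gate → gate | 27 → 15% | 39 → 24% | 51 → 34% |
| Bonferroni over three: no gate → gate | 22 → 14% | 33 → 23% | 44 → 33% |
| 8-point gain sustained at follow-up, over two | 27 → 17% | 40 → 28% | 50 → 40% |
| Mean brace-versus-control estimate when the gate opens, as a multiple of the truth | 1.7 | 1.5 | 1.4 |

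The losses in percentage points are 12, 15 and 17 over two contrasts; 8, 10 and 11 over three; and 10, 12 and 10 over two with a sustained effect.

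**Step 4: error control.** With no true effect in any arm, two Bonferroni contrasts alone have a family-wise error of about 4.5–4.7%. With the gate added it is about 2%. The gate is not needed to hold 5%.

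**Step 5: sensitivity.** With a true gain of 12 points the exaggeration is about 1.1 to 1.4 times at 10 to 20 per arm, and 1.04 times at 30. At 30 per arm, a sustained 0.8 SD effect and correlation 0.7, it is 1.00 times, and power for a given arm moves only from 95.8% to 95.7%.

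**Step 6: the literal gate.** The sentence admits any main effect. Adding an assumed common recovery of 10 points at post and 15 at follow-up in every arm makes the time effect significant in essentially 100% of trials. Estimates given that time or group × time is significant then average 1.00–1.01 times the truth, and no power is lost.

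**The case against.** The strongest reply is that the text does less harm than it seems to. It says that post-hoc analysis follows a significant effect; it does not say that estimates are withheld otherwise. The model comparison of arms and the descriptive statistics are unconditional, and the group × time coefficients of a fitted model can be read as differences from control with standard errors. This stands. A reader might infer that a non-significant omnibus test leaves the trial with no effect estimate, but the documents do not say so. What remains is that no such contrast or interval is promised.

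A reader might also infer that the filter bites whichever term decides. Step 6 shows otherwise: it depends on the deciding effect being group × time, which the plan does not state. If time may decide, the gate has no function, and leaving the choice open allows it to be made after the data are seen.

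The 4 degrees of freedom assume that the resistance arms are kept apart. The singular wording of the Analytic Plan permits pooling, and then the figures above do not apply.

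Exaggeration is not peculiar to the gate. Under the same assumptions, ungated contrasts that reach 0.025 average 2.06, 1.75 and 1.55 times the truth. Dropping the gate alone would therefore not cure selection; reporting every estimate does.

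Finally, an omnibus test followed by adjusted comparisons is conventional and controls error, and the stated objective is a hypothesis test. That is fair, but the hypothesis is a directed contrast with control, which can be tested directly at the same error rate.

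**Conclusion.** The point holds in a limited form. The plan prespecifies no contrast with control and no interval, and its one formal route to arm comparisons is an adjusted step behind a gate whose deciding effect is not stated.

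If that effect is group × time with unpooled arms, the two layers are more conservative than needed. Under the assumed values they cost roughly 8 to 17 percentage points of success in at least one arm at 10 to 20 per arm, and gated estimates run about 1.4 to 1.7 times the truth. Every one of these sizes rests on assumed sample size, SD, correlation and effect; with larger samples or effects they fall almost to nothing. The claim that the trial would necessarily report either nothing or an inflated effect goes beyond the documents. The change is still worth making, because it improves the plan under each reading of the gate.

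**What to change.** Replace the gate sentence in the Analytic Plan with:

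> For each outcome, the difference from control in change from pre-intervention, for each resistance arm [or: for the pooled resistance arms], at post-intervention and at follow-up, will be estimated from the mixed model and reported with its 95% confidence interval whatever the overall tests show. For the primary outcome, the pre-to-post contrast(s) with control will be tested directly, with Dunnett or Holm adjustment if there are two, without a preceding omnibus test.

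The sponsor should keep one bracketed option, so that the Analytic Plan agrees with the three arms in Study Design for ACLR subjects, and should name one adjustment method.

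The cost is a change of wording and a few more rows in the results table, with no new data or patients. The small downside is that other arm differences, such as brace versus band, become descriptive.
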